8.2 Key Secondary Endpoint

ORR is defined as the proportion of patients with a confirmed complete response (CR) or partial response (PR) based on the independent radiologic review and during the initial assigned study treatment. This analysis will be performed in the ITT population as the main analysis and the PP population as supportive analysis. To be assigned a status of a CR or PR, changes in tumor measurements must be confirmed by repeat assessments that must be performed at least 4 weeks (allowing a minus 3 day window) after the criteria for response are first met. This analysis will include assessments prior to an event or censoring under the primary PFS analysis. Patients with unknown or missing response will be categorized as non-responders and will be included in the denominator when calculating the proportion. An unstratified two-sided Fisher's Exact test at a 0.05 significance level will be used to investigate statistical differences between treatment groups.

A 95% Newcombe score confidence interval will be constructed for the treatment rate difference in ORR ([Newcombe, 1998](#))

A sensitivity analysis will be performed for ORR without requiring confirmation of CR and PR.

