8 EFFICACY ANALYSIS

8.1 Primary Efficacy Analysis

The primary endpoint of PFS (reported in weeks) is defined as the interval between the date of randomization and the earliest documented evidence of the first disease progression based on the independent radiologic review or death due to any cause on initially assigned study treatment, whichever comes earlier. In the following situations, PFS will be re-defined otherwise or censored:

- For patients who do not have evaluable radiologic assessment (including those randomized but untreated due to death or any other cause), PFS will be censored at randomization date (PFS=1 day) unless they die within 2 cycles of treatment (8 weeks plus 3 days allowing for a late radiologic assessment within the visit window). If patients die within 2 cycles of treatment (8 weeks plus 3 days), they are considered to have a PFS event at death date
- For patients who only have non-measurable lesion according to modified RECIST Version 1.1 (non-nodal lesions must be ≥ 1.0 cm in the long axis or \geq double the slide thickness in the long axis) within 21 days prior to the first dose of study treatment, PFS will be censored at the date of latest evaluable progression-free radiologic assessment or patients will be considered to have disease progression at the date of new lesion(s) or unequivocal progression in non-target disease
- For patients who undergo surgical resection of target or non-target lesions, who have received other anticancer treatments than the study treatment before documented date of the first disease progression, PFS will be censored at the date of the latest evaluable progression-free radiologic assessment
- For patients who have not progressed and have not died, PFS will be censored at the time of the latest date of evaluable progression-free radiologic assessment if at most one missed/non-evaluable assessment prior to this assessment
- For patients who have first disease progression or die after two or more consecutive missed/non-evaluable assessments, the patient will be censored at the time of the evaluable radiologic assessment immediately prior to the two or more consecutive missed/non-evaluable radiologic assessments. The missed/non-evaluable assessments include both the scheduled assessments when a patient was on treatment and the hypothetical assessments (the expected assessments as if the patient was still on

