8.5 Multiple Comparisons/Multiplicity

To control familywise type-I error, the hypothesis tests for treatment difference between DCC-2618 and placebo will be performed at two-sided 0.05 level of significance sequentially in the following order:

1. The primary endpoint PFS based on independent radiologic review
2. The key secondary endpoint ORR based on independent radiologic review
3. OS
4. QOL as determined by changes from baseline to Day 1 of Cycle 2 in EORTC-QLQ-C30 Role function and Physical function (each at 0.025 level of significance)

If any hypothesis test is not significant at $\alpha=0.05$ level, the subsequently listed analyses will be viewed as descriptive.

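### The ORR rule in SAP 8.2, read literally, excludes the scan on which PFS is censored, so a responder first confirmed on that scan counts as a non-responder in the test that gates OS

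*SAP*

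**What the plan says.** **ORR window (SAP 8.2).** "This analysis will include assessments prior to an event or censoring under the primary PFS analysis". A CR or PR needs a repeat assessment at least 4 weeks later, with a 3-day allowance. "Patients with unknown or missing response will be categorized as non-responders", and they stay in the denominator. The comparison is "An unstratified two-sided Fisher's Exact test at a 0.05 significance level". A sensitivity analysis drops the confirmation requirement.

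**PFS censoring date (SAP 8.1).** For a patient with at least one evaluable scan, the date is always that of a scan:
- No progression and no death: "PFS will be censored at the time of the latest date of evaluable progression-free radiologic assessment".
- Resection or other anticancer treatment before progression: "PFS will be censored at the date of the latest evaluable progression-free radiologic assessment".
- Progression or death after a gap: "the patient will be censored at the time of the evaluable radiologic assessment immediately prior to the two or more consecutive" missed or non-evaluable scans.

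A patient with no evaluable scan who does not die within the stated early window is censored at randomization.

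**Hierarchy (SAP 8.5).** The second step is "The key secondary endpoint ORR based on independent radiologic review". OS follows, then QOL. If a step is not significant, everything after it is descriptive.

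**The concern.** The two sections do not fit together at the boundary. Excluding assessments from the event date onward is right for a PFS event, because the progression scan must not count towards response. For a censored patient the boundary scan is valid progression-free data, and it may be the scan that confirms a response. If it is left out, only the first response scan remains, the response is unconfirmed, and the patient goes into the denominator as a non-responder.

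The patients exposed are responders without a counted PFS event whose confirmation is recent. Such patients are to be expected when the cut-off is driven by events, and most would be on DCC-2618. ORR decides whether OS and QOL are tested formally. There is also a specification risk: two programmers could derive different ORR counts from the same sentence, and the reading could end up being chosen after the data are seen.

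**Working it through.** **1. The plan's own ORR figure.** Protocol 9.1 and SAP 2.3 state about 80% power with 70 versus 35 patients and rates 0.22 versus 0.02. Exact enumeration with the planned two-sided Fisher test at 0.05 gives 85.0% at 70/35 and 90.1% at 80/40. The stated figure is not reproduced but is conservative for the planned test. The point does not depend on it.

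**2. The boundary, by example.** Inputs: 28-day cycles, with scans every cycle through Cycle 4 and every other cycle after that (Protocol Table 1). Day 1 of Cycle k falls 28 × (k − 1) days after Cycle 1 Day 1, so scans fall at days 28, 56, 84, 140, 196 and so on. Take a patient with a first PR at day 84, a PR again at day 140, and data cut-off at day 160.
- The interval is 140 − 84 = 56 days, which exceeds 28 − 3 = 25 days, so the PR is confirmed.
- The PFS censoring date under SAP 8.1 is day 140.
- Literal SAP 8.2 admits days 28, 56 and 84. These contain one PR scan, so the patient is a non-responder.
- Inclusive reading: day 140 counts, so the patient is a responder.
- If cut-off is at day 200 instead, and day 196 is evaluable and progression-free, censoring moves to day 196. Day 140 is then before it, and the patient is a responder under both readings.

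So a response is lost only if no evaluable progression-free scan follows the first confirming scan before censoring. On the later schedule the next scan is 56 days away, so the exposure is not brief.

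**3. What one patient does to the test.** The two-sided Fisher p-value sums the probabilities of all tables with the same margins that are no more probable than the one observed. With 9 responders among 120, all on DCC-2618:
- upper tail C(80,9)/C(120,9) = 0.0222
- tables with 0 to 2 responders on DCC-2618 = 0.0063
- total 0.0284 (unrounded tails)

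With 8 responders, all on DCC-2618: 0.0345 + 0.0163 = 0.0508.

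| DCC-2618 (n=80) vs placebo (n=40) | p | One DCC-2618 responder fewer | p |
|---|---|---|---|
| 9 vs 0 | 0.028 | 8 vs 0 | 0.051 |
| 13 vs 1 | 0.033 | 12 vs 1 | 0.058 |
| 14 vs 0 | 0.0046 | 13 vs 0 | 0.0045 |
| 14 vs 1 | 0.019 | 13 vs 1 | 0.033 |

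The first two rows cross 0.05; the last two do not.

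**4. How many responders could be lost.** From the documents: 80/40, medians 4.5 and 1 month, 22% and 2% response, 9 months of uniform accrual, the scan schedule, and cut-off at 90 PFS events. Assumed, because the documents give neither: first response at Cycles 2/3/4/6/8 in 30/25/20/15/10% of responders, and a median response duration of 7 months.
- Confirmed DCC-2618 responders average about 14.3 with the censoring scan and 13.0 without it, a loss of 14.3 − 13.0 = 1.3, or 1.3/14.3 = 9%.
- At least one is lost in about 73% of simulated trials.
- The chance that ORR passes falls from about 76% to 69%. The 76% is below the 90.1% in step 1 because the 22% is applied here before confirmation, and 14.3/80 = 17.9% are confirmed by cut-off.
- Under the other onset and duration assumptions tried, the mean loss is about 0.6 to 1.8, the chance of any loss about 41% to 84%, and the fall in the chance of passing about 3 to 12 percentage points. These are scenarios, not bounds.

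**5. Cross-check without a simulation.** Remove an assumed share of responders in both arms and recompute exact Fisher power:

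| Share lost | 70/35 | 80/40 |
|---|---|---|
| 0% | 85.0% | 90.1% |
| 5% | 81.9% | 87.6% |
| 10% | 78.5% | 84.5% |
| 20% | 70.8% | 76.9% |

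A 10% loss costs 90.1 − 84.5 = 5.6 points at 80/40, the same order as the 76 − 69 = 7 points in step 4.

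**The case against.** The best answer is that this is a loose preposition, not a decision to discard data. The sentence can be read as cutting off scans after progression, resection, new therapy or a gap. The rest of the plan supports that: SAP 8.1 calls the boundary scan evaluable and progression-free, SAP 8.3.7 censors duration of response at that kind of scan, SAP 8.3.3 follows time to response to the last assessment in the double-blind period, and Protocol 9.8.5.2.1 has no such window. This stands as evidence of intent. It does not supply the missing words. It also shows an inconsistency: under the literal rule the same patient can be a confirmed responder in time to response and a non-responder in ORR.

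Four stronger readings are tempting, and the documents do not support them.
- *Every censored patient loses a usable scan and may lose a response.* Patients without an evaluable scan are censored at randomization and have no response to lose. Among the rest, only a responder whose first confirming scan is the censoring scan changes status. Scans after a gap are excluded under either reading.
- *The 73% is the chance that the gate fails.* It is the chance of losing at least one responder under assumed inputs. At the simulated averages, 14 or 13 versus 0 or 1, every comparison is significant. The 9-versus-8 cliff lies near 9/80 = 11%, half the planned 22%.
- *The ORR test is biased towards DCC-2618.* The literal rule only removes responders, mostly from the arm expected to have more, so it is conservative.
- *Time to response and duration of response need the same repair.* Neither section contains this sentence. Putting a PFS-based window into SAP 8.3.3 would change its censoring rule.

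The sensitivity analysis without confirmation would usually count an affected patient, because the first response scan precedes censoring. That softens the descriptive picture, but it cannot open the gate to OS.

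**Conclusion.** The concern holds as a boundary error in SAP 8.2. As written, the rule turns a validly confirmed responder into a non-responder when the first confirming scan is the PFS censoring scan. The effect is a lower ORR and lower power for the gate to OS and QOL, mainly through DCC-2618, with no inflation of type I error. Under the inclusive reading, which was probably intended, the effect is zero.

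Under the literal reading the size rests on response onset and duration, which the documents do not give. The assumed values tried lose about 0.6 to 1.8 DCC-2618 responders on average and cost about 3 to 12 points of the chance that ORR passes. A single patient is decisive only near the critical value. The case for acting does not depend on these figures: an alpha-controlled endpoint should have one derivation, fixed in advance.

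**What to change.** In SAP 8.2 only, and before unblinding, replace the window sentence with:

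> This analysis will include assessments before the date of the PFS event or, for patients censored for PFS, on or before the PFS censoring date.

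This still excludes the progression scan, and it still excludes scans after resection, after other anticancer treatment or after a gap of two or more missed scans. Leave SAP 8.3.3 and 8.3.7 as they are.

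The cost is one sentence and the matching line in the ORR programming specification. No design figure changes: Fisher power stays at 85.0% (70/35) or 90.1% (80/40). If the literal exclusion was in fact intended, the SAP should say so and give the reason.

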8.3 Secondary Efficacy Analysis

8.3.1 Time to Progression

TTP (reported in weeks) is defined as the interval between the date of randomization and the earliest documented evidence of first disease progression on initial treatment based on the independent radiologic review. Since dying without progression is a competing risk of progression, TTP is censored at death date for patients who died without disease progression. Additionally, in the following situations, PFS will be re-defined otherwise or censored:

- For patients who do not have evaluable radiologic assessment, TTP will be censored at randomization date (TTP=1 day) unless they die within 2 cycles of treatment (8 weeks plus 3 days allowing for a late radiologic assessment within the visit window).

If patients die within 2 cycles of treatment (8 weeks plus 3 days), TTP will be censored at death date

- For patients who only have none measurable lesion according to modified RECIST Version 1.1 (non-nodal lesions must be ≥ 1.0 cm in the long axis or \geq double the slide thickness in the long axis) within 21 days prior to the first dose of study treatment, TTP will be censored at the date of latest evaluable progression-free radiologic assessment or patients will be considered to have disease progression at the date of new lesion(s) or unequivocal progression in non-target disease
- For patients who undergo surgical resection of target or non-target lesions, who have received other anticancer treatments than the study treatment before documented date of the first disease progression, TTP will be censored at the date of the latest evaluable progression-free radiologic assessment
- For patients who have not progressed, TTP will be censored at the time of the latest date of evaluable progression-free radiologic assessment if at most one missed/non-evaluable assessment prior to this assessment
- For patients who have first disease progression after two or more consecutive missed/non-evaluable scheduled or hypothetical assessments, TTP will be censored at the time of the evaluable radiologic assessment immediately prior to the two or more consecutive missed/non-evaluable scheduled or hypothetical radiologic assessments
- For patients who have first disease progression documented between scheduled assessments, progression date is defined as the date of new lesion (if progression is due to new lesions) or defined as the earliest of the scan dates of the components that triggered the progression per independent radiologic review (if progression is due to increase in sum of measured lesions)

TTP will be analyzed in a similar fashion to PFS.

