6.10.2. Overall Survival Follow-Up by Phone Call

All patients will be followed until withdrawal of consent or death from any cause. After the Safety Follow-Up Visit, patients will be contacted every 3 months (± 1 month) to collect long-term survival data.

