9.8.5.3. Secondary Endpoints

9.8.5.3.1. Time to Tumor Progression

The secondary endpoint of TTP (reported in weeks) is defined as the interval between the date of randomization and the earliest documented evidence of disease progression based on the independent radiologic review. Patients who undergo surgical resection of target or non-target lesions, who have received other anticancer treatments, who do not have a documented date of progression or death due to any cause, or who die prior to tumor progression will be censored at the date of the last assessment. P-value for treatment difference will be obtained using the log rank test. Hazard ratio will be from a Cox regression model and its 95% confidence intervals will use Wald method.

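### SAP 8.3.1 censors time to progression at death, while the protocol and another SAP 8.3.1 bullet use the last scan; the rules need reconciling, and the effect on this secondary endpoint is modest

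*SAP*

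**What the plan says.** Protocol 9.8.5.3.1 lists, among the patients censored for TTP, those "who die prior to tumor progression will be censored at the date of the last assessment". SAP 8.3.1 calls death without progression a competing risk and states that "TTP is censored at death date for patients who died without disease progression". Its first bullet uses the death date again, for patients with no evaluable scan who die within 8 weeks plus 3 days.

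The fourth bullet of the same section reads: "For patients who have not progressed, TTP will be censored at the time of the latest date of evaluable progression-free radiologic assessment". It applies if at most one assessment was missed beforehand, and it does not set deaths aside. The matching PFS bullet in SAP 8.1 does: "For patients who have not progressed and have not died, PFS will be censored".

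The rules for gaps in imaging also differ. For PFS: "For patients who have first disease progression or die after two or more consecutive missed/non-evaluable assessments, the patient will be censored". For TTP the bullet covers only progression after the gap: "For patients who have first disease progression after two or more consecutive missed/non-evaluable scheduled or hypothetical assessments".

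Protocol Table 1 schedules imaging through the end-of-treatment (EOT) visit and none in safety or survival follow-up. Deaths are still collected by phone under protocol 6.10.2: "All patients will be followed until withdrawal of consent or death from any cause". Under SAP 3.1, the double-blind period of a patient without reviewed progression runs to the last follow-up date, so deaths after treatment has stopped fall inside it.

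**The concern.** Progression is seen only on scans, so a patient's progression status is known only up to the last evaluable one. Censoring at a later death date keeps the patient in the risk set for time in which nobody was scheduled to look. TTP counts only progression on initial treatment, so the added time after stopping can hardly produce an event. The progression hazard is then understated and the Kaplan-Meier TTP percentiles are too long. The extra time also depends on a later outcome: two patients stop on the same day after the same clean scan, and only the one who dies gains progression-free time.

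Separately, the text leaves the derivation open. A death without progression meets both the general sentence and the fourth bullet, which give different dates, so two programmers could produce different TTP datasets. SAP section 1 says the SAP outlines its differences from the protocol's methods, but 8.3.1 does not flag this one.

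**Working it through.** **1. The rules side by side, for a patient with at least one evaluable scan**

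| Situation | Protocol TTP | SAP TTP | SAP PFS |
|---|---|---|---|
| Alive, no progression | last assessment | latest evaluable scan | latest evaluable scan |
| Dies, no progression, fewer than two missed scans | last assessment | death date (sentence) or latest evaluable scan (fourth bullet) | event at death |
| Dies, no progression, two or more missed scans | last assessment | death date; gap bullet does not apply | censored at scan before the gap |
| Other anticancer therapy or resection first | last assessment | latest evaluable scan | latest evaluable scan |

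The last row limits the problem: off treatment, it concerns patients who stop without reviewed progression, have neither new therapy nor resection, and die before the data cut-off.

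**2. One worked patient (assumed dates).** Scans fall at about weeks 4, 8, 12, 20 and 28 (each cycle to Cycle 4, then every other cycle). The patient stops for a reason other than progression, has a clean EOT scan at week 9 and no new therapy, and dies at week 30.
- Protocol TTP: censored at week 9.
- SAP PFS: the expected scans at weeks 12, 20 and 28 are missed, so censored at week 9.
- SAP TTP by the death-date sentence: censored at week 30.
- Added time: 30 − 9 = 21 weeks, or 21 / 4.348 = 4.8 months.
- Same patient alive at week 30: TTP censored at week 9.

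**3. Deaths on treatment.** With all scans done, the gap from last scan to death is at most about 4 weeks up to week 12 and about 8 weeks after that.

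**4. The plan's own figure.** The documents give no figure for TTP, so the PFS assumptions set the time scale (medians 4.5 and 1 month, 9 months' uniform accrual plus 6). With λ = ln 2 / median, P(event) = 1 − [exp(−6λ) − exp(−15λ)] / (9λ).
- DCC-2618: λ = 0.1540, P = 0.7853, and 70 × 0.7853 = 54.97 events.
- Placebo: λ = 0.6931, P = 0.9975, and 35 × 0.9975 = 34.91 events.
- Total 89.9, which reproduces the stated 90 (55 + 35).

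**5. Size by hand.** The hazard estimate is events / person-time, so adding A event-free weeks to T weeks lowers it by A / (T + A). For 70 patients, T = 54.97 / 0.1540 = 357 months = 1,552 weeks; for 80 patients, 1,552 × 80/70 = 1,774 weeks. Simulating 80 patients with 2–6% per month stopping, median survival of 3–6 months afterwards and no new therapy gave A of about 57–179 weeks:
- 57 / (1,774 + 57) = 3.1%
- 179 / (1,774 + 179) = 9.2%

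Stopping shortens T, and the simulated fall was accordingly 3–11%.

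**6. Size by simulation.** DCC-2618 arm, exponential time to progression with median 4.5 months, protocol scan schedule, 15-month cut. Assumed: median survival after stopping 3–6 months; none to half start new therapy.

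| Stopping without reviewed progression | Fall in progression hazard | Rise in mean KM median |
|---|---|---|
| about 3% per month (near the 15% dropout, 0.15 × 80 = 12 patients) | about 3–5% | about 0.4–1.1 weeks |
| 6% per month | about 5–10% | about 1.2–2.5 weeks |

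**7. Between arms.** With both arms simulated under still heavier stopping (about 28% or 44% leaving treatment per 26 weeks, median 8–26 weeks to death, no new therapy), the hazard ratio moved from about 0.23 to 0.24–0.26, and the DCC-2618 median rose by about 1.5–3.4 weeks.

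**The case against.** The strongest objection is that the bullets modify the general sentence. They are introduced as situations in which the endpoint is re-defined or censored differently, so the fourth bullet may override the death-date sentence, and then there is little inflation. That reading is available, and the bias is therefore conditional. It does not settle the text: the lead-in offers the bullets as additional and names PFS instead of TTP, the fourth bullet applies only with at most one missed assessment, and the first bullet repeats the death date.

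Censoring at death is also ordinary practice when death precludes the event, which is the SAP's stated reason. That suits an event observed continuously. Here the SAP itself stops at the last evaluable scan for TTP in living patients, for censored duration of response, and for PFS after a gap.

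Unscheduled assessments are allowed (protocol 6.6) and used for efficacy (SAP 3.4). That stands: the accurate statement is that no imaging is scheduled after EOT, not that progression could never be recorded.

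A reader might infer that TTP is generally inflated by months, or that the rule flatters DCC-2618. The documents support neither. Months arise only for off-treatment deaths without new therapy or resection, and the simulated hazard ratio moves toward 1. Even the median often stays put, because it can only fall on scan dates: with 4% per month stopping it was unchanged in 81–84% of simulated trials.

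**Conclusion.** The inconsistency is real and should be corrected. SAP 8.3.1 departs from protocol 9.8.5.3.1, conflicts with its own fourth bullet, and lacks the cap on unscanned time before death that SAP 8.1 provides for PFS.

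If the death-date sentence governs, the progression hazard is modestly understated and the Kaplan-Meier TTP estimates modestly inflated: about 3–5% and 0.4–1.1 weeks with stopping near the planned dropout, and about 5–10% and 1.2–2.5 weeks at 6% per month. These rest on assumed rates of stopping, survival afterwards and new therapy, none of which the documents give, and on the PFS median standing in for TTP. If the fourth bullet governs, the distortion largely disappears and the ambiguity remains.

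It would be wrong to read this as a threat to the main results. TTP is not in the testing sequence of SAP 8.5, so PFS, ORR, OS and familywise error are unaffected. One caveat: the SAP cites protocol Amendment 5, and the amendment number of the supplied protocol cannot be confirmed from its text.

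**What to change.** In SAP 8.3.1:
- Replace both death-date rules with censoring at the latest evaluable progression-free radiologic assessment, consistent with protocol 9.8.5.3.1. If there is none, censor at randomization. That fallback follows the SAP's own no-scan rule; the protocol section does not contain it.
- Add *or die* after *progression* in the two-missed-assessment bullet, as in SAP 8.1, and state that where such a gap exists the scan before the gap is used. Without this, a clean scan after a gap would leave two possible dates.
- Correct the lead-in so that it refers to TTP, not PFS.
- If death-date censoring is wanted, keep it as a named sensitivity analysis.

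The cost is a wording change and one derivation. No new data are needed.
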